## Statistical Analysis

We powered the study for a small effect size given our hypothesis that tDCS would be associated with a relevant reduction in craving scores. Thus, assuming a small effect size of 0.3 specified for SPSS in G\*Power 3.1 for a repeated measure (5 measures) within-between interaction analysis of variance (ANOVA) as principal statistical test for the craving analysis with a power of 80%, a two-sided probability of a type I error of 5%, a minimum of 38 subjects would be necessary; however to account for waiving or dropouts expected to be very common in this condition, we increased the estimated sample to approximately 20%, resulting in 45 to 46 subjects (22 to 23 subjects in each group).

Age, patterns of alcohol use and 5-items OCDS were normally distributed according to D'Agostino & Pearson normality test, thus they were analyzed by parametric tests.

Besides the two-way ANOVA (sham-tDCS and tDCS groups as between-subjects factor) with repeated measures (five time-points as within-subjects factor) followed by Bonferroni's multiple comparisons as *post-hoc* test, linear regression analyses were done over craving scores obtained over the respective five time-points for both groups and the slopes of the respective curves were compared using a modified version of the *t* test according to Zar (1984), which is equivalent to analysis of covariance. Additional comparisons between initial and final OCDS scores were done by paired *t* tests for each group, and differences between final and initial scores were compared between sham-tDCS and tDCS groups with unpaired *t* tests. Effect sizes were calculated using Cohen's *d* and corrected by Hedges's  $g_s$  for unpaired and Hedges'  $g_{av}$  for paired *t*-tests (Lakens, 2013).

Age and patterns of alcohol use were compared between groups by unpaired *t*-test. For all other non-parametric data, Chi-square or Fisher tests were used to compare results between sham and real tDCS groups.

A two-tailed p-value of 0.05 or less was considered to indicate statistical significance. SPSS Statistics Base 24.0 (SPSS Inc, USA) and GraphPad Prism 7.0

(GraphPad Software Inc, USA) were employed for statistical analysis and graphic presentations.

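### The change-score comparison of craving leaves out baseline adjustment, which would make it more precise, and no sphericity correction is stated for the principal group-by-time ANOVA

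*Combined protocol and SAP*

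**What the plan says.** All the relevant text is in the Statistical Analysis section of the combined protocol and SAP.

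- **Principal test.** The craving analysis rests on a "within-between interaction analysis of variance (ANOVA) as principal statistical test for the craving analysis with a power of 80"%. It has two groups and five measurements.
- **Sample size.** For that test "a minimum of 38 subjects would be necessary", raised for dropout, "resulting in 45 to 46 subjects (22 to 23 subjects in each group").
- **Further tests of the same score.** "Besides the two-way ANOVA (sham-tDCS and tDCS groups as between-subjects factor) with repeated measures (five time-points as within-subjects factor"), the plan compares regression slopes over the five time points, a method "which is equivalent to analysis of covariance". "Additional comparisons between initial and final OCDS scores were done by paired" t tests within each group, and "differences between final and initial scores were compared between sham-tDCS and tDCS groups with unpaired" t tests.
- **Assumptions.** Normality is the only assumption check reported. Sphericity, epsilon, a Greenhouse-Geisser or Huynh-Feldt correction, and a multivariate alternative are not mentioned.
- **Software.** The plan lists "SPSS Statistics Base 24.0 (SPSS Inc, USA) and GraphPad Prism 7.0" without saying which of them gave the principal p value.

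The measurement 1 score is taken in the week before stimulation starts (section on the craving assessment), so a baseline covariate is available. The analysis of covariance named in the plan has time as its covariate. No planned analysis uses the measurement 1 score as a covariate.

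**The concern.** Two separate matters are involved, and they differ in kind.

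**Precision of the between-group change comparison.** Subtracting the measurement 1 score fixes its coefficient at 1. Unless the true regression slope of final on initial score is 1, this adds noise. It also over-corrects any chance baseline imbalance: with equal SDs and correlation 0.5, half of the imbalance stays in the estimate with its sign reversed. At stake is the width of the interval, not validity.

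**Type I error of the principal test.** The uncorrected F test of the interaction holds its 5% level only if all pairwise differences between visits have equal variance. Weekly scores are neighbours, while the first and last are roughly three to four and a half weeks apart, so correlation that fades with time is plausible. If it fades and no correction was made, the error rate would exceed 5%. The software list does not settle whether a correction was made.

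**Working it through.** **Inputs from the documents.** Two arms at 1:1 (Procedures); five measurements, effect size 0.3 in the SPSS convention, two-sided 5%, 80% power, N = 38 raised to 45 to 46 (Statistical Analysis). The calculations use 22 per arm (N = 44). Correlations, covariance patterns and effect shapes are assumptions, because the documents give none.

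**Step 1. The plan's own figure.** Noncentral F with df1 = 4e, df2 = 4e(N − 2), λ = 0.09 × (N − 2) × 4e, where e is epsilon. At e = 1, N = 36 gives power 0.796 and N = 38 gives 0.822, so 38 is reproduced for equal arms. By the same formula 80% power is kept down to e = 0.716 at N = 45 and 0.692 at N = 46.

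**Step 2. Change score against baseline adjustment.** With equal SD σ at both measurements and correlation ρ:

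- change-score variance: 2σ²(1 − ρ)
- adjusted variance: σ²(1 − ρ²)
- ratio: (1 + ρ)/2, times 1 + 1/(N − 4) = 1 + 1/40 = 1.025 for estimating the slope

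| Assumed ρ | Variance ratio | Variance lower by | Interval narrower by |
|---|---|---|---|
| 0.3 | 0.65 × 1.025 = 0.666 | 33% | 1 − √0.666 = 18% |
| 0.5 | 0.75 × 1.025 = 0.769 | 23% | 12% |
| 0.7 | 0.85 × 1.025 = 0.871 | 13% | 7% |

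Simulated ratios were 0.668, 0.768 and 0.871. If the SDs differ (σ1 initial, σ5 final), the change-score variance exceeds the adjusted one by (σ1 − ρσ5)², before the slope cost. The gain is then never negative, but it shrinks towards zero as ρσ5 approaches σ1.

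In power terms, take equal correlation 0.5 and a linear divergence reaching 1.04 SD (40,000 simulated trials). The change-score test has 92.3% and the adjusted test 97.0%.

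**Step 3. Spacing of the measurements.** Ten sessions every other day run from day 1 to day 19, a span of 18 days. Measurement 1 is 1 to 7 days before and measurement 5 is 1 to 7 days after. The gap is therefore 18 + 1 + 1 = 20 to 18 + 7 + 7 = 32 days.

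**Step 4. Type I error of the interaction test with no group effect, 22 per arm** (60,000 to 100,000 simulated trials per setting; 40,000 for random slopes).

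| Assumed covariance | Epsilon | Uncorrected | Greenhouse-Geisser |
|---|---|---|---|
| Equal correlation 0.3, 0.5, 0.7 | 1 | 5.0% to 5.1% | 4.4% to 4.5% |
| Autoregressive mixed with measurement error, or with error and stable patient differences (16 settings) | 0.89 to 0.98 | 5.0% to 5.6% | 4.3% to 4.6% |
| Pure autoregressive 0.3 | 0.92 | 5.5% | 4.5% |
| Pure autoregressive 0.5 | 0.81 | 6.3% | 4.7% |
| Pure autoregressive 0.7 | 0.69 | 7.2% | 4.8% |
| Pure autoregressive 0.9 | 0.58 | 7.9% | 4.8% |
| Marked random slopes | 0.57 | 7.8% | 4.7% |

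In the mixed rows, error was 20% to 50% of the variance and stable patient differences 0% to 40%.

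**Step 5. When a correction would change the conclusion.** The critical F at 22 per arm is 2.43 uncorrected (df 4 and 168). It is 2.61, 2.76 and 2.94 at epsilon 0.81, 0.69 and 0.58. Only an observed F between 2.43 and the corrected value changes the conclusion.

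**The case against.** **The plan's silence is not evidence of an uncorrected test.** The section is a summary written in the past tense, and a correction may have been applied. This stands. A reader might infer that the principal test ran at 7% to 8%, and the documents do not support that. They show neither an uncorrected F nor any correlation, and fading correlation alone does not produce such figures. At autoregressive 0.9, 30% assumed measurement error brings the error from 7.9% to about 5.5%. A five-item self-report scale plausibly carries such error. In those mixed cases Greenhouse-Geisser, at 4.3% to 4.6%, is about as far from 5% on the other side.

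**The sample size.** A reader might also infer that the trial is undersized because 38 presumes near-sphericity. It is not: the planned number is 45 to 46, which by Step 1 keeps 80% power down to an epsilon of about 0.7.

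**Baseline adjustment is optional refinement.** The change-score test is valid under randomisation, is labelled additional, and did not drive the sample size. Comparing per-patient slopes without baseline reaches 96.6% power in the linear scenario, against 97.0% for the adjusted final score. For a mid-course effect (0, 0.4, 0.9, 0.9, 0.4 SD) the adjusted final score has 32% power and the ANOVA 82%. These points stand and are why the ANOVA should remain principal. They do not remove the gain over the change-score test, which has 25% in that scenario. The trial already reports a final-minus-initial contrast, and the same data can give it a tighter interval.

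**Conclusion.** The point holds as two inexpensive improvements. It does not show an invalid analysis.

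1. The between-group change-score test is valid but gives up precision: 13% to 33% of the variance for correlations of 0.7 to 0.3 at 22 per arm. This assumes equal SDs at the two measurements; the gain is smaller if the final SD is clearly larger. The plan's mention of analysis of covariance does not fill the gap, because it concerns slopes over time.
2. The handling of sphericity in the principal test is unstated. If no correction was applied, the excess over 5% lies between nothing and about 3 points, with the upper end confined to strong pure autoregressive correlation or marked random slopes. The conclusion is affected only if F falls between about 2.4 and at most about 2.9.

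Confidence is moderate, since every correlation and covariance pattern here is assumed.

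**What to change.** **1. Add the baseline-adjusted comparison.** Beside the planned change-score t test, report an analysis of covariance of the measurement 5 score on group and measurement 1 score, with the adjusted difference and its 95% interval. Label it as set after data collection: recruitment ended in January 2018 and the plan already reports normality results. It costs one degree of freedom and replaces nothing.

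**2. State how sphericity was handled.** Keep the ANOVA as principal, report the estimated epsilon, and base the group-by-time conclusion on the Greenhouse-Geisser p value. If a correction was already used, one sentence naming it is enough; if it is new, label it as set after data collection. In the linear scenario of Step 2 it costs about 1 point of power under sphericity (88.1% to 87.0%). At autoregressive 0.7 the fall is about 6 points (78.8% to 73.2%), but the first of those figures comes from a test that exceeds its 5% level.

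Both changes need only SAP wording and a re-analysis of data in hand.

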#### *Craving assessment: 5-items OCDS*

Craving was scored with a brief scale composed of 5 items (1, 2, 4, 5, and 13) from the Obsessive-Compulsive Drinking Scale (OCDS) (21-23), which assesses craving in a narrow sense according to De Wildt et al. (24).

Questions of this brief scale allow quantification of thoughts and feelings (obsessions), and behavioral intentions (24), and are answered on a scale ranging from 0 to 4, resulting in a total score between 0 and 20. They ask how much of a person's time (total per day), when the drug is not used, is occupied by thoughts, ideas, desires, or impulses related to alcohol and its effects; how frequently these thoughts, ideas, desires, or impulses related to alcohol and its effects occur; how much distress or disturbance these ideas, thoughts, impulses or desire related to alcohol use cause when the person is under withdrawal; how much effort the person has to make to resist these thoughts, ideas, desires, or impulses, or how much energy he/she has to spend to think of something else when they enter the mind under withdrawal; and finally ask about the person's drive to use alcohol.

This scale was applied in the week before the beginning of the real or sham-tDCS treatment (1st measurement), during the treatment over approximately 3-weeks (2nd, 3rd and 4th measurements) and in the week after the end of the brain stimulation protocol (5th measurement).

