### *Procedures*

Those patients who were eligible for study participation according to the inclusion and exclusion criteria described above and agreed to participate in this study signed an informed consent form (Fig. 1). All data were originally acquired from participants participating in a randomized sham-controlled double-blind clinical trial to investigate the efficacy of tDCS treatment of alcohol dependence.

After global physical and clinical examination, subjects were randomly assigned to one of the two intervention groups (sham- and real tDCS) in a 1:1 ratio using a computer-generated block randomization sequence that was kept with the unblinded study coordinator (not involved in recruitment) and only revealed to the co-investigator conducting treatments immediately before the first session.

Craving (5-items OCDS) was measured before and after completion of the treatment and once per week during the three-weeks treatment, resulting in five measurements (Fig. 1). Alcohol use relapses after hospital discharge were verbally obtained from patients, families or caregivers.

Participants and experimenters were blinded for brain stimulation assignments from the beginning of the study protocol up to the end of the 3-months follow-up after the end of sham-tDCS or real tDCS treatment, configuring a double-blind experimental design.

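### Post-hoc craving comparisons use single-step Bonferroni over an unlisted family; Holm's procedure keeps the same 5% familywise bound and is never less powerful

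*Combined protocol and SAP*

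**What the plan says.** All references are to the combined protocol and SAP.

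- **Principal test** (Statistical Analysis): the "within-between interaction analysis of variance (ANOVA) as principal statistical test for the craving analysis". The sample size is built on this test.
- **Post-hoc step** (same section): the ANOVA is specified with "repeated measures (five time-points as within-subjects factor) followed by Bonferroni's multiple comparisons". The section does not say which pairs are compared (arms within a time point, time points within an arm, or all cells) or how many comparisons the correction counts.
- **Timing** (Craving assessment): for the first measurement, "This scale was applied in the week before the beginning of the real or sham-tDCS treatment". Procedures confirms the schedule: craving was "measured before and after completion of the treatment and once per week during the three-weeks treatment, resulting in five measurements". One measurement is therefore pre-treatment and four are on or after treatment.
- **Other craving tests** (Statistical Analysis): a comparison of regression slopes, paired t tests of first against last score within each arm, and an unpaired t test between arms on final-minus-initial change. No multiplicity adjustment is stated for these. The general rule is "A two-tailed p-value of 0.05 or less was considered to indicate statistical significance".

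**The concern.** Two features of the post-hoc step cost power without tightening the guaranteed error rate.

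First, single-step Bonferroni holds every comparison to alpha divided by the family size, even after others have been rejected. Holm relaxes the threshold as rejections accumulate and keeps the same familywise guarantee.

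Second, the time factor includes a measurement taken before any stimulation. Under randomisation, an arm difference there can only be chance. If that contrast is in the family, it takes a share of the 5% and cannot show a tDCS effect.

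What is at stake is modest. The interaction F test does not show at which measurements the arms separate; the post-hoc contrasts do. With 22 to 23 patients per arm, a few points of power on those contrasts are worth having if they need no new data.

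**Working it through.** **1. The plan's own figure.** Inputs from Statistical Analysis: "assuming a small effect size of 0.3 specified for SPSS", 2 groups, 5 measures, alpha 0.05, power 80%. With the SPSS-type effect size and sphericity, df1 = (2-1)(5-1) = 4, df2 = (N-2)(4) and lambda = f² x (N-2) x 4. At N = 38, lambda = 0.09 x 36 x 4 = 12.96 and power is 82.2%. N = 37 gives 80.9% and N = 36 gives 79.6%, so 38 is the smallest even N reaching 80%. The stated figure reproduces. The post-hoc adjustment does not enter this calculation.

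**2. Why Holm is never worse on the same family.** Order the m p-values and compare them in turn with alpha/m, alpha/(m-1), ..., alpha, stopping at the first failure. Every threshold is at least alpha/m, so whatever Bonferroni rejects, Holm rejects. For error control, suppose m0 nulls are true. The first true null to be rejected is preceded by at most m - m0 rejections, so it faces a threshold of at most alpha/m0. The Bonferroni inequality over the m0 true nulls then gives at most alpha, whatever the correlation. This holds for any family the sponsor intended.

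**3. Thresholds if the family is the five between-arm contrasts (assumption).** Bonferroni: 0.05/5 = 0.0100 each. Holm over measurements 2 to 5: 0.0125, 0.0167, 0.025, 0.05.

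**4. Power at measurement 5.** Assumptions: 23 versus 22 patients (the plan's 22 to 23 per arm), normal scores, equal variances, unpaired t tests on raw scores, between-time correlation 0.5 to 0.7, true difference 0.8 SD at measurement 5. The Bonferroni figure has a closed form: noncentrality = 0.8 x sqrt(23 x 22/45) = 2.68 on 43 df, against a critical value of 2.70, giving about 50%. The Holm figures are from simulation.

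| Procedure | Linear build-up | Constant from measurement 2 |
|---|---|---|
| Bonferroni over five | about 50% | about 50% |
| Holm over all five | about 51% | 56-57% |
| Holm over measurements 2-5 | 54-55% | 62-63% |

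For 0.6 and 1.0 SD, Bonferroni over five gives about 26% and 74%. Holm over measurements 2 to 5 gives about 30% and 78% (linear) or 35% and 85% (constant).

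**5. Effect scaled to the plan's lambda of 12.96.** At 19 per arm, from Bonferroni over five to Holm over four:

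| Correlation | Linear | Constant |
|---|---|---|
| 0.3 | 85.8% to 89.1% | 74.3% to 86.4% |
| 0.5 | 69.3% to 73.7% | 55.5% to 68.7% |
| 0.7 | 42.0% to 46.3% | 32.0% to 42.3% |

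The gain is about 3 to 13 points. For the constant effect at correlation 0.5, it splits as Bonferroni-5 55.5%, Bonferroni-4 58.8%, Holm-5 62.2%, Holm-4 68.7%, so both the smaller family and the step-down contribute. In that setting, power to detect all four contrasts rises from 24.0% to 50.4%. Power for at least one rises only from 84.8% to 87.0%, which comes from the smaller family alone.

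**6. Familywise error.** With no effect anywhere (correlation 0.3 / 0.5 / 0.7): Bonferroni-5 0.048 / 0.044 / 0.037; Holm-4 0.048 / 0.045 / 0.038. With large effects at measurements 4 and 5 only: Bonferroni-5 0.024 to 0.028; Holm-4 0.043 to 0.049. Both stay under 0.05; Holm uses more of it.

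**7. What the plan already does at end of treatment.** The change-score t test is run at 0.05. The SD of change is SD x sqrt(2(1 - rho)), so 0.8 SD becomes 0.8 at correlation 0.5 and 0.8/sqrt(0.6) = 1.03 at 0.7. Power with 23 versus 22 is about 75% and 92%.

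**The case against.** **The family is not stated.** A reader might infer that the plan does test the arms at baseline and so wastes a fifth of its alpha, or that it corrects for all 45 pairs of the 2 x 5 cells (10 x 9/2 = 45). The text supports neither. It gives a five-level factor and the name of a correction. If the comparisons are within-arm against baseline, measurement 1 is the necessary reference and nothing is wasted. This stands: the baseline part of the point is conditional. Holm's advantage on a given family is not.

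**The end-of-treatment contrast is not short of power because of Bonferroni.** The change-score test, with about 75% to 92% power at 0.8 SD, exceeds every Holm figure for that difference in step 4. This stands, and it limits the practical gain to the time course.

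**The step is secondary.** A reader might infer that the sample size or the main conclusion is compromised. It is not: Bonferroni is valid and the interaction test is unchanged.

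**Holm is not free of consequence.** It spends more of the 5% when some nulls are false. The slope, paired and change-score tests have no stated adjustment, so neither procedure controls error over all craving tests. Both remarks are right; neither breaks the 5% bound within the post-hoc family.

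**The timing is late.** The Participants section reports recruitment from June 2015 to January 2018 and two dropouts. A switch now to a more liberal procedure needs disclosure. This stands and is reflected in the fix.

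**Conclusion.** The point holds as an optional efficiency improvement to a secondary step, not as an error. Holm on the same family is never less powerful than the stated method at the same 5% bound; this rests on no assumption about the trial.

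The size of the gain does rest on assumptions: a family of five between-arm contrasts, and the correlations and effect shapes tried. For a 0.8 SD difference it is about 4 to 5 points at measurement 5 under linear build-up and about 12 to 13 under a constant effect, when the baseline contrast is also dropped. Holm alone, over all five, adds about 1 point or 6 to 7 points. Since the change-score test already addresses end of treatment, the benefit lies mainly in showing when the arms differ.

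**What to change.** Replace the post-hoc wording with: *Post-hoc p-values will be adjusted by Holm's step-down procedure; between-arm comparisons will be made at measurements 2 to 5 only, with measurement 1 used as the baseline reference and not tested between arms.* List any within-arm contrasts that are kept and Holm-adjust them too, so that the family is explicit.

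Cost: a sentence or two of wording and a re-run of the comparisons, with no new data. Holm gives no simple simultaneous confidence intervals; unadjusted 95% intervals, labelled as such, can stand beside the adjusted p-values. Because the text describes completed work, the Holm results should be labelled post hoc.

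### The supplementary slope comparison treats five craving scores per patient as independent, so as written its p-value is not valid in general, in a direction the documents do not fix.

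*Combined protocol and SAP*

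**What the plan says.** All references are to the combined protocol and SAP.

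- **Data.** Procedures: "Craving (5-items OCDS) was measured before and after completion of the treatment and once per week during the three-weeks treatment". That makes five scores per patient.
- **Principal test.** Statistical Analysis powers the trial on a "within-between interaction analysis of variance (ANOVA) as principal statistical test for the craving analysis". Time is declared there as a repeated, within-patient factor: "Besides the two-way ANOVA (sham-tDCS and tDCS groups as between-subjects factor) with repeated measures (five time-points as within-subjects factor".
- **Slope test.** In the same sentence, as an addition to that ANOVA, "linear regression analyses were done over craving scores obtained over the respective five time-points for both groups". Then "the slopes of the respective curves were compared using a modified version of the" t test, taken from a cited 1984 source, "which is equivalent to analysis of covariance". No patient effect, per-patient slope or correlation structure is mentioned. The text does not say whether the points regressed were individual scores or group means.
- **Other between-group test.** "differences between final and initial scores were compared between sham-tDCS and tDCS groups with unpaired" t tests.
- **Threshold.** "A two-tailed p-value of 0.05 or less was considered to indicate statistical significance". No exception is made for the slope test.

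**The concern.** An ordinary comparison of two regression slopes takes its standard error from the scatter about the fitted lines and treats every point as independent. Five scores from one patient are not independent. The section recognises this for the ANOVA, then describes a second test of much the same question without it.

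The slope p-value is read at 0.05 like the others, but its true error rate may be well below or above 5%. A reader could take a significant slope difference as extra support, or a non-significant one as contrary evidence, with no sound basis for either.

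**Working it through.** **1. The plan's own figure.** The documents give no figure for the slope test. Their sample size belongs to the ANOVA. With effect size f = 0.3, k = 2 groups and m = 5 measures, the SPSS-type noncentrality is f²(N − k)(m − 1). At N = 38 this is 0.09 × 36 × 4 = 12.96, on 4 and 144 df, giving power 82.2%. N = 37 gives 80.9%, and equal groups round it to 38. Then 38 × 1.2 = 45.6, which matches 45 to 46. The stated size is reproduced without the slope test.

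**2. Inputs.** From the documents: five visits, 1:1 allocation, 22 to 23 per group, two-sided 5%. Assumed, because the documents give none: equally spaced visits, normal scores, the within-patient correlation and the shape of the mean course.

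**3. Pooled individual scores.** Code visits as t = −2, −1, 0, 1, 2, so Sxx = 10. With complete data the arm slope is the mean of the patients' own slopes.
- True variance of the slope difference: 2 Var(bᵢ)/n, where bᵢ is one patient's slope.
- Variance the test uses: 2s²/(10n), with s² close to the average variance of a score, on 5N − 4 df. That is 221 df at N = 45 and 226 at N = 46, so it counts scores rather than patients.
- Ratio R = 10 Var(bᵢ) / average score variance. Approximate null error: 2Φ(−1.96/√R).

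For equal correlation ρ, R = 1 − ρ. For first-order autoregressive ρ, R = (10 + 8ρ − 2ρ² − 8ρ³ − 8ρ⁴)/10.

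| Structure | R | Approximate error | Simulated error |
|---|---|---|---|
| Equal 0.3 | 0.70 | 1.9% | 2.0% |
| Equal 0.5 | 0.50 | 0.6% | 0.7% |
| Equal 0.7 | 0.30 | 0.03% | about 0.1% |
| Autoregressive 0.3 | 1.19 | 7.3% | 7.3% |
| Autoregressive 0.5 | 1.20 | 7.4% | 7.6% |
| Autoregressive 0.7 | 1.00 | 5.0% | 5.5% |
| Autoregressive 0.9 | 0.45 | 0.3% | 0.5% |

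The simulations use 40,000 null trials per row, 23 per arm. Independent repeats agree within about 0.3 points.

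**4. Pooled scores with patient-specific slopes.** Slope SD 0.2 to 0.4 per visit, intercept variance 0.25 to 1, residual SD 1. The error is about 1.4% to 7.3%, apart from three cases at 9% to 13%. All three place the time origin at the middle visit and imply a negative correlation between a patient's first and last score. For the highest (slope SD 0.4, intercept variance 0.25), the covariance is 0.25 − 4 × 0.16 = −0.39 and the variance is 0.25 + 0.64 + 1 = 1.89, so the correlation is −0.21.

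A second grid (intercept and residual variance both 0.5, slope SD up to 0.5) ran from 1.0% to 17.0%. Values above 8.3% again arose only where that correlation is negative.

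**5. Group means.** Ten means less four parameters leave 6 df.

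| Mean course | Equal correlation | Autoregressive 0.3 to 0.9 | Patient-specific slopes (step 4, first grid) |
|---|---|---|---|
| Straight line | about 5% | 10% to 30% | 8% to 18% |
| Shared steep early decline | 0.1% or less | 0.0% to 0.7% | 0.7% to 3.3% |
| Shared milder curve | 1.6% to 2.9% | 7% to 13% | about 6% to 15% |

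The steep decline is 0, −0.8, −1.1, −1.2, −1.25 SD; the milder one is 0, −0.45, −0.8, −1.05, −1.25 SD. Curvature shared by the arms goes into the residual and pushes the error down. On the second grid, straight-line means gave 6.6% to 36.2%.

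**6. One slope per patient, unpaired t test.** 4.6% to 5.3% in every scenario. The change-score t test gives 4.7% to 5.2%.

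**The case against.** **The test is supplementary.** This stands. The section names the ANOVA as principal, and nothing in the documents shows a conclusion resting on the slope p-value. The point is therefore minor.

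**A patient term may have been used and not described.** This stands in part. The documents show what was described, not what was computed. But they name a specific test, and that test followed as written has the wrong standard error. If something else was done, one sentence settles it.

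**The correlations are assumed.** True, and unavoidable. The ranges show what can happen, not what did.

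**The large error rates need particular conditions.** This stands. With pooled scores, 9% and above appears only where first and last scores are negatively correlated, which is implausible for repeated craving scores. The 10% to 30% figures need group means, serial correlation and straight-line courses, and the text speaks of scores and does not mention means. Equal correlation is also not a necessary condition for a near-nominal test on means: with the milder curve and slope SD 0.2 the error is about 6%.

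**Pooling is often cautious, hence harmless.** This does not stand. At equal correlation 0.7, with 19 per arm and a linear separation reaching 0.8 SD at visit 5, the pooled test has 51% power against 93% for per-patient slopes.

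A reader might infer that ignoring the pairing inflates false positives. The documents do not support that, because under a constant within-patient correlation the pooled test errs the other way.

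**Conclusion.** The concern holds, as a minor one. The described slope test assumes independence that five scores per patient do not have, so its p-value is not valid in general. Neither the size nor the direction of the error can be fixed from the documents. Confidence is high that the described method has this fault. The percentages hold only under the assumed correlations, mean shapes, equal spacing and normality.

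A reader might also infer that the trial's craving result is compromised. The documents do not support this: the principal ANOVA declares time as a within-patient factor, the change-score test uses one number per patient, and the sample size of 38 comes from the ANOVA alone.

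**What to change.** - Replace the slope test with one least-squares slope per patient, compared between arms by unpaired t test. Report the slope difference with its confidence interval. Label it a post hoc replacement, since the analyses are described as already done.
- If visits are missing, use instead one mixed model with group-by-time, a patient random intercept and slope, and small-sample degrees of freedom. Participants reports two dropouts after randomization. In a check with 10% of visits missing at random, such a model gave 4.1% to 5.7% null error (Monte Carlo SE 0.5 to 0.6 points).
- Otherwise show the fitted slopes descriptively, without a p-value, and state what was regressed.
- Keep the slope comparison supplementary to the principal ANOVA.

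**Cost.** A short re-run on existing data, or the loss of one p-value; no new patients or measurements. A slope captures only a linear trend. If a 0.8 SD separation is complete by visit 2 and then flat, at equal correlation 0.5 and 19 per arm, per-patient slopes have 58% power against 67% for the change score.
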